## **12.9 Publication Policy**

The results of this study will be published by the study investigator and sub-investigators.

The Sponsor requires review of written and oral presentation at least 45 days prior to initial submission to the publishing authority. If necessary to protect proprietary rights of information to be disclosed in the publication, the Sponsor may request a further 45 day delay in submission for publication, and the investigators agree to make all reasonable efforts to grant such further delay to the Sponsor.

## 14 APPENDIX 1: Patient Evaluation Flow Sheet – Treatment Phase

Each INDUCTION and CONSOLIDATION:

Day:	Screening	1	2	3	4	5	6	7	10	14	21	28	35	42	Weekly  ±2	150  ±10	End of Phase/Early Term. ±30
Informed Consent 	x																
Medical/Leukemia History	x																
Physical Exam	x							x		x							
Vital Signs	x							x		x							
ECOG Performance Status	x																
ECG	x														x	x 	
Registration	x																
Hematology	x		x					x		x	x	x	x	x	x	x	
Biochemistry	x		x				x	x		x	x	x	x	x	x	x	
Urinalysis	x																
Bone Marrow Evaluation	x														x 	As needed to confirm response/persistence	
Chest X-ray/Chest CT	x																
Echocardiography/MUGA/cardiac MRI	x														x	x	x
Blessed Orientation Concentration															x 	x 	
MOCA	x 							x 							x 	x 	
FACT-Leu	x 							x 							x 	x 	
Response Assessment											x 						
Cytogenetics/Molecular Studies	x																
Adverse Events																	
Concomitant Medications																	
Treatment Administration	CPX-351														x		

The first induction may end prematurely if a second induction is necessary, see Section 4.4. The schedule of evaluations for the first induction is followed until the second induction starts, then the evaluations are followed as indicated in the flow sheet, beginning with Day 1

Second inductions and consolidations of are CPX-351 on Days 1 and 3, see Sections 4.4 & 4.5, See Section 7 for an alternative consolidation regimen of intermediate dose cytarabine, e.g. for patients that exceed 500mg/m^2 cumulative daunorubicin-equivalent dose, or as decided by the investigator

Continue weekly evaluations until confirmation of response (CR/CRi) or persistent disease is declared

Within 30 days prior to start of screening, if informed consent was collected, 30 days elapse and the patient is still not screened he/she must sign another ICF  
Required after first induction (in case the Day 14 bone marrow is non-evaluable or assessment of aplasia is equivocal, a repeat evaluation may be performed 5-14 days later, at the discretion of the treating physician, in order to determine effect and need for second induction

Day 150 or 45 Days after the last treatment whichever is later

See Section 9.3, Repeat ECHO/MUGA/cardiac MRI before the second consolidation

ECG will be performed pre-dose for each course of treatment, and at the end of each course or EOT.

Blessed, MOCA and FACT-Leu can be administered +/- 3 days from indicated day

## 15 APPENDIX 2: Patient Evaluation Flow Sheet –Follow-up

		Monthly for 1 Year (±10 Days)	Once Years 2-5	Early Termination
Patient status report		x	x	x
Hematology		x	x	x
Biochemistry		Perform monthly only if abnormality(ies) persists at the end of the Treatment Phase. Perform until abnormality(ies) returns to baseline, until 1 year from registration, or the initiation of new therapy and/or relapse. (whichever is earliest)		
Bone Aspiration/Biopsy	Marrow	For patients in CR or CRI perform at any time that there is a suspicion of relapse. For patients in CR, perform if peripheral blood counts fall below 1000/ $\mu$ L for ANC or 100,000/ $\mu$ L for platelets for >1 month or at any time there is suspicion of relapse. For patients in CRI perform if counts fall significantly below peak recovery levels. If the peripheral blood counts in a patient with a CRI recover to CR levels ( $\geq$ 1000/ $\mu$ L for ANC or $\geq$ 100,000/ $\mu$ L for platelets), perform a bone marrow evaluation within 14 days to confirm CR. Following the first year of follow up, record relapse information, including any bone marrow evaluations. Not required following the initiation of new therapy and/or relapse.		
Echocardiography, MUGA or Cardiac MRI		If last LVEF treatment phase or Day 150 was reduced >10% from baseline and is less than 50% repeat every 3 months until LVEF returns to baseline ( $\pm$ 5%) or until 1 year from registration. Persistent reductions in LVEF of >10% with nadir values below 50% documented at 1 year are considered permanent sequelae.		
Adverse Events/Toxicity		Assess AEs that were ongoing at the time of discontinuation. Do NOT record any new AEs. AEs that persist without evidence of recovery for >30 days are considered permanent sequelae and do not require further follow-up.		

**16 APPENDIX 3: Performance Status – ECOG**

Grade	Description
0	Fully active, able to carry on all pre-disease performance without restriction (Karnofsky 90-100)
1	Restricted in physically strenuous activity but ambulatory and able to carry out work of a light or sedentary nature (e.g., light housework, office work) (Karnofsky 70-80).
2	Ambulatory and capable of all self-care but unable to carry out any work activities. Up and about more than 50% of waking hours (Karnofsky 50-60).
3	Capable of only limited self-care, confined to bed or chair more than 50% of waking hours (Karnofsky 30-40).
4	Completely disabled. Cannot carry on any self-care. Totally confined to bed or chair (Karnofsky 10-20).

**17 APPENDIX 4: Common Terminology Criteria for Adverse Events  
V4.0 (CTCAE)**

This 72 page document can be obtained as a pdf file from <http://ctep.cancer.gov>.  
The publication date is June 14, 2010

**18 APPENDIX 5: Elements of the HIPAA Privacy Rule Authorization**

- Written in plain language understandable to the patient or the representative;
- A “specific and meaningful” description of Protected Health Information (PHI) to be used and disclosed;
- The specific identification of the person/class authorized to make the use or disclosure;
- The specific identification of the persons/class to whom the covered entity may make the requested use or disclosure;
- Description of the purpose of the disclosure;
- An expiration date or event (i.e., “no expiration date” for data repository use, or “for the duration of a specific research study” permits use until end of study plus time for wrapping up and reporting);
- A statement of the patient’s right to revoke the authorization and any exceptions to the right to revoke;
- Conditions, if any, on authorization;
- A statement about possible re-disclosures of PHI by the recipient and that the PHI will no longer be protected by the Privacy Rule in the event of such re-disclosures; and
- The signature and date of the patient (or of the patient’s personal representative, along with the personal representative’s authority to act).

## **19 APPENDIX 6: Declaration of Helsinki**

WORLD MEDICAL ASSOCIATION DECLARATION OF HELSINKI ETHICAL PRINCIPLES  
FOR MEDICAL RESEARCH INVOLVING HUMAN SUBJECTS  
(Available at <http://www.wma.net/en/20activities/10ethics/10helsinki/>)

## 20 APPENDIX 7: Anthracyclines Equivalents Guidelines

According to the exclusion criteria patients with a total lifetime anthracycline exposure exceeding the equivalent of 368 mg/m^2 of daunorubicin (or equivalent) prior to start of study therapy [100 u/m^2 of CPX-351 contains 44 mg/m^2 of daunorubicin x 3 doses (1 induction) = 132 mg/m^2 + 368 mg/m^2 = 500 mg/m^2 = maximum allowable limit of daunorubicin from all sources at the end of the 1st induction] are excluded from Protocol CLTR0310-301.

	Conversion factor*
Daunorubicin	1
Doxorubicin	2
Epirubicin	1
Idarubicin	4
Mitoxantrone	4.4

Multiply the number in the second column by the total cumulative dose a patient has received.

For example:

200mg/m^2 of mitoxantrone x 4.4(conversion factor) = 880mg/m^2

This means 200mg/m^2 of mitoxantrone is equivalent to 880 mg/m^2 of daunorubicin

\*Adapted from Keefe D., Anthracycline-Induced Cardiomyopathy. Seminars in Oncology, Vol 28, No 4, Suppl 12 (August), 2001: pp 2-7

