## 4.4 Repeat of Induction

Patients achieving aplasia/hypoplasia (<5% blast count) will not receive second inductions. Patients with reduced tumor burden and evidence of persistent leukemia who remain fit for additional intensive chemotherapy can be given second inductions up to 60 days (measured from day 1 of chemotherapy treatment) after the first induction treatment date.

Patients unable to achieve a response (CR, CRp, or CRi) after up to 2 inductions are discontinued from further treatment and followed for survival.

Dosing for second induction:

- CPX-351 at 100 u/m^2 will be administered on days 1 and 3

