## 4.5 Consolidation Therapy

Only patients with confirmed response (CR or CRp or CRi) and who remain fit for additional chemotherapy are eligible for chemotherapy consolidation. Investigators may

use post remission therapy of their choice or they may choose to use CPX-351. Before consolidation treatment can begin, patients need a repeat echocardiogram and labs to evaluate renal and liver function and must fulfill eligibility criteria initiation of treatment. For patients given CPX-351 post remission therapy: prior to starting consolidation, LVEF must be documented to be  $\geq 50\%$  and patients must have recovered to ANC  $> 500/\mu\text{L}$  and platelets  $> 50,000/\mu\text{L}$  within 56 days after last dose of CPX-351. A second consolidation cycle is permitted provided the first consolidation course was well tolerated and repeat echocardiogram shows an LVEF  $> 50\%$  and ANC and platelets have recovered within 56 days of the start of the last consolidation cycle. Up to 2 consolidation courses are permitted. Scheduling and dose of consolidation treatment may be adjusted depending on degree and rate of patient recovery.

Dosing for consolidation:

- CPX-351 at 65  $\text{u}/\text{m}^2$  will be administered on days 1 and 3

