#### *5.1.2 Exclusion Criteria*

- 5.1.2.1 Acute promyelocytic leukemia [t(15;17)]
- 5.1.2.2 Clinical or morphologic evidence of active CNS leukemia
- 5.1.2.3 Prior intensive chemotherapy for AML with anthracycline/cytarabine-based regimens and/ or prior HSCT. Patients may have been treated with commercially available or investigational hypomethylating agents (e.g. decitabine, azacitidine, SGI-110), lenalidomide, or low-dose cytarabine (not to exceed 20 mg/m^2 daily for 14 days for  $\leq$  6 cycles)
- 5.1.2.4 Prior treatment including HMA, systemic chemotherapy, surgery, or radiation therapy must have been completed at least 7 days before start of study treatment or after discussion with PI. Treatment with investigational agents must have been completed at least 14 days prior to study drug treatment. Hydroxyurea is permitted for control of blood counts before the start of study treatment. Toxicities associated with prior therapies must have recovered to grade 1 or less prior to start of study treatment.
- 5.1.2.5 Patients with prior cumulative anthracycline exposure of greater than 368 mg/m^2 daunorubicin (or equivalent).
- 5.1.2.6 Any serious medical condition, laboratory abnormality or psychiatric illness that would prevent obtaining informed consent
- 5.1.2.7 Patients with myocardial impairment of any cause (e.g. cardiomyopathy, ischemic heart disease, significant valvular dysfunction, hypertensive heart disease, and congestive heart failure) resulting in heart failure by New York Heart Association Criteria (Class III or IV staging)
- 5.1.2.8 Active or uncontrolled infection. Patients with an infection receiving treatment (antibiotic, antifungal or antiviral treatment) may be entered into the study but must be afebrile and hemodynamically stable for  $\geq$ 72 hrs.

- 5.1.2.9 Patients with current or recent evidence of invasive fungal infection (blood or tissue culture); patients with recent fungal infection must have a subsequent negative cultures to be eligible
- 5.1.2.10 Known HIV (new testing not required) or evidence of active hepatitis B or C infection (with rising transaminase values)
- 5.1.2.11 Hypersensitivity to cytarabine, daunorubicin or liposomal products
- 5.1.2.12 History of Wilson's disease or other copper-metabolism disorder
- 5.1.2.13 History of prior bone marrow or solid organ transplantation

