### **7.5 Duration of Protocol Treatment**

Patients may continue on study provided they have not met the criteria for discontinuation of therapy (See Section 5.2). Patients may receive up to 2 induction courses followed by up to 2 consolidation courses. After the Treatment Phase, patients will be followed for up to 5 years.

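### For courses after the first induction, the dosing sections name no cumulative daunorubicin-equivalent check, and the only later-course mention of 500 mg/m² points to a Section 7 regimen that is not there

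*Combined protocol and SAP*

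**What the plan says.** **Entry.** Exclusion 5.1.2.5 bars "Patients with prior cumulative anthracycline exposure of greater than 368" mg/m² of daunorubicin or equivalent. Appendix 7 explains the figure: 368 plus the first induction makes 500 mg/m², the "maximum allowable limit of daunorubicin from all sources at the end of the 1st induction". It also gives conversion factors for other anthracyclines.

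**Second induction (4.4).** "Patients with reduced tumor burden and evidence of persistent leukemia who remain fit for additional intensive chemotherapy can be given second inductions", within a 60-day window. No dose total and no LVEF result is named as a condition.

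**Consolidation (4.5).** Investigators may "use post remission therapy of their choice or they may choose to use CPX-351". For CPX-351, "prior to starting consolidation, LVEF must be documented to be" at least 50%, with count recovery. A second consolidation needs LVEF above 50%, count recovery and a well-tolerated first course. No cumulative dose is named. Patients also "must fulfill eligibility criteria initiation of treatment", without saying which criteria.

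**Number of courses (7.5).** "Patients may receive up to 2 induction courses followed by up to 2 consolidation courses".

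**Appendix 1, footnote 2.** "See Section 7 for an alternative consolidation regimen of intermediate dose cytarabine". Exceeding 500 mg/m² cumulative daunorubicin equivalent is offered as an example of when to use it; the investigator's decision is the other stated ground. Section 7 lists only CPX-351 regimens.

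**The concern.** The protocol takes the trouble to work back from 500 mg/m² to an entry cap. Once the first induction is over, its dosing sections no longer mention the total. A site working from Sections 4.4, 4.5 and 7 could take an eligible patient past the dose at which footnote 2 points to a different consolidation, and those sections contain no step at which anyone adds up the exposure. A site that does read the footnote is sent to a regimen it will not find, and must guess whether *exceed* means already above 500 or above 500 once the planned course is given.

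Those at stake are patients with substantial anthracycline exposure from another disease. Therapy-related AML and prior malignancy in remission are eligible (5.1.1.6, 5.1.1.14), while prior intensive anthracycline/cytarabine-based treatment for AML is excluded (5.1.2.3). The issue is individual cardiac safety. Overall survival and 30-day mortality are defined and analysed without reference to cumulative dose.

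**Working it through.** **Inputs.** 0.44 mg daunorubicin per unit (Section 2.2, Table 1). Doses from Sections 4.3 to 4.5 and the Section 7 tables. Entry cap 368 mg/m² (5.1.2.5).

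**Daunorubicin per course** (u/m² × 0.44 × number of doses):

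- First induction, I1: 100 × 0.44 × 3 = 132 mg/m²
- Second induction, I2: 100 × 0.44 × 2 = 88 mg/m²
- Each consolidation, C: 65 × 0.44 × 2 = 57.2 mg/m²

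**The plan's own figure.** 368 + 132 = 500 mg/m². Appendix 7 reproduces exactly.

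**What the later courses add.** 88 + 2 × 57.2 = 202.4 mg/m².

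**Totals under the dosing sections alone (mg/m²):**

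| Courses | On-study sum | Total from 368 | Prior exposure above which the path passes 500 |
|---|---|---|---|
| I1 | 132 | 500 | 368 (not possible within the cap) |
| I1 + C | 189.2 | 557.2 | 310.8 |
| I1 + I2 | 220 | 588 | 280 |
| I1 + 2C | 246.4 | 614.4 | 253.6 |
| I1 + I2 + C | 277.2 | 645.2 | 222.8 |
| I1 + I2 + 2C | 334.4 | 702.4 | 165.6 |

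The last column is 500 minus the on-study sum.

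**Effect of footnote 2.** Its alternative regimen concerns consolidation only, so 588 after two inductions stands on any reading. The consolidation totals depend on the reading:

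- *Not applied:* every row is reachable, up to 702.4.
- *Applied to patients already above 500:* a patient at the cap has exactly 500 after I1, so the footnote does not bar a first consolidation, and 557.2 is reachable. Totals above 588 are not.
- *Applied counting the planned course:* no full-dose consolidation ends above 500.

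**Trigger points.** A full-dose consolidation passes 500 when the sum before it is above 500 − 57.2 = 442.8. At a reduced dose of d u/m² on two days the trigger is 500 − 0.88d, which is higher. A second induction passes 500 when the sum is above 500 − 88 = 412.

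**Who can be affected.** Patients with no prior anthracycline reach at most 132 + 202.4 = 334.4 mg/m². The lowest prior exposure of concern, 165.6, converts with the Appendix 7 factors to 165.6/2 = 82.8 mg/m² doxorubicin, 165.6/4 = 41.4 idarubicin or 165.6/4.4 = 37.6 mitoxantrone.

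**Are the data there?** Prior chemotherapy is taken at screening (6.1), exclusion 5.1.2.5 already requires a converted total, and each CPX-351 dose is charted (7.1.1.2). What the dosing sections lack is the instruction to add them and act on the result.

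**The case against.** The best defence is that footnote 2 already contains the check for consolidation. It cannot be applied without summing the dose, Appendix 7 supplies the factors, and if *exceed* is taken to include the planned course it does all that is needed. On this view the rule is misplaced and badly cross-referenced rather than missing. That is fair, and it limits the point. It does not settle which reading a site will use, and it does not reach the second induction.

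Heart function is also watched directly. LVEF is a condition for every CPX-351 consolidation (4.5). Imaging is scheduled after the last induction and before each consolidation (6.2) and at end of treatment (6.3), with repeats every three months after a marked fall (6.4). There are ECGs with each course, cardiac AE and SAE rules (9.3), DSMB review of the Day 30 echocardiogram (11.7), withdrawal for harm (5.2) and discretion over dose (7.3, and 4.5 for consolidation). A reader might infer that patients go past 500 mg/m² unmonitored; the documents do not support that. None of these safeguards is triggered by dose, however.

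Two further inferences should be resisted. One is that 500 mg/m² is a ceiling for the whole trial which the dosing schedule breaches: Appendix 7 ties it to the end of the first induction, and footnote 2 uses it as an example. The other is that the eligibility phrase in 4.5 re-imposes 368 before consolidation as a second, conflicting limit: Appendix 7 defines 368 as exposure before study therapy starts, so on-study doses would not count towards it.

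Finally, allowing 588 after a second induction while redirecting consolidation at 500 looks uneven. The difference is defensible. A second induction treats persistent leukaemia, and 4.4 names no substitute. A consolidation patient is in remission, and 4.5 already offers another therapy.

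**Conclusion.** The point holds in a narrow form. For courses after the first induction, Sections 4.4, 4.5 and 7 name no cumulative daunorubicin-equivalent check. The one later-course use of 500 mg/m² sits in a footnote that cites a regimen not present and leaves the planned course unaddressed. From the entry cap, 588 mg/m² is permitted however the footnote is read; 557.2 is permitted if the footnote is not applied or is read as covering only patients already above 500; 702.4 requires cap-level prior exposure, all four courses at full dose and the footnote not being applied.

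That few of the 30 patients will be affected is a judgement: the documents give no distribution of prior anthracycline exposure, but passing 500 needs more than 165.6 mg/m² from earlier treatment. The documents also give no cardiac risk by cumulative dose for this liposomal product, so harm from crossing 500 is not shown. The argument rests only on the protocol's own threshold. Neither primary endpoint changes. The grade is minor to should-fix, justified by how little the correction costs.

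**What to change.** 1. Before the second induction and before each CPX-351 consolidation, sum the recorded prior and on-study doses using the Appendix 7 factors.
2. Move the footnote 2 rule into Section 4.5 and state that it counts the planned course. Patients whose total would exceed 500 mg/m² (sum above 442.8 at the full consolidation dose, higher if the dose is reduced as 4.5 allows) receive the non-CPX-351 post-remission therapy that 4.5 already permits.
3. Point footnote 2 to Section 4.5 instead of Section 7.
4. In Section 4.4, have the investigator review the summed dose before a second induction (above 412 means it will pass 500), together with any LVEF result available. Set no new ceiling there.

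The entry cap stays as it is and no echocardiogram is added. The cost is a wording amendment to 4.4, 4.5 and footnote 2, plus one added figure before each later course; no extra patients, visits or procedures. The downside is that a few heavily pre-exposed patients would receive non-CPX-351 consolidation.
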